- a) The patient will be PN dependent and at risk for significant hepatic injury due to prolonged use of parenteral nutrition.
- b) Have significant hepatic dysfunction due to parenteral nutrition despite utilization of all conventional therapies.

Inclusion Criteria:

1. Patients will be PN dependent (unable to meet nutritional needs solely by enteral nutrition) and are expected to require PN for at least another 30 days
2. Patients considered eligible for study participation must have parenteral nutrition associated liver disease (PNALD) as defined as a direct bilirubin of ≥ 2 mg/dl or currently on Omegaven through another protocol. Other causes of liver disease should be excluded. A liver biopsy is not necessary for treatment.
3. Direct bilirubin > 2.0 mg/dl, or already on Omegaven through another protocol.
4. Signed patient informed consent.
5. The patient must have utilized standard therapies to prevent the progression of his/her liver disease including surgical treatment, cyclic PN, avoiding overfeeding, reduction/removal of copper and manganese from PN, advancement of enteral feeding, and the use of ursodiol (i.e., Actigall[®]).

Exclusion Criteria:

1. Pregnancy
2. Other causes of chronic liver disease (Hepatitis C, biliary atresia, and alpha 1 anti-trypsin deficiency,)
3. Enrollment in any other clinical trial involving an investigational agent (unless approved by the designated physicians on the multidisciplinary team)
4. The parent or guardian or child unwilling to provide consent or assent

In rare instances, patients diagnosed with PNALD may later be found to have liver disease due to other causes in addition to the use of PN (i.e., inborn errors of metabolism, viral infections). Such causes may not be known at the time of enrollment and will not preclude them from continuing in the study. For the sake of statistical analysis, however, these patients will be excluded although all data will be collected and reviewed.

Screening Procedures

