A second analysis will be done using more contemporary historical controls from patients receiving conventional PN. This will include 50 patients (approximately 10 per year) retrospectively enrolled and previously treated with soybean based emulsions from 1999-2004. Subjects will be selected among patients with surgical gastrointestinal diseases and will have been expected to need PN for 30 days or more at the beginning of PN administration. For the retrospective soybean cohort, to make their selection process comparable to the prospectively enrolled Omegaven® cohort, we will apply the inclusion criteria to the records at moment that cholestasis develops (i.e., direct bilirubin ≥ 2 mg/dL) making no assumptions based upon the outcomes of their actual PN course. Unlike prior analyses comparing Omegaven® treated patients with PNALD with those receiving only soybean fat emulsions, this cohort is expected to be more contemporary with less variability in the standards of care as the study period only covers 4 years rather than 12 year period examined by Andorsky et al. A request for research limited to the use of medical records/charts and computer databases was submitted and approved by the Committee on Clinical Investigations on July 25, 2007. (M07-07-0312).

Inclusion Criteria:

1) Age < 2 years; 2) Be PN dependent (unable to meet nutritional needs solely by enteral nutrition); 3) Present PNALD, as evidenced by two consecutive direct bilirubin ≥ 2.0 mg/dL; 4) Have failed standard therapies to prevent the progression of his/her liver disease that may include surgical treatment, cyclic PN, avoiding overfeeding, reduction/removal of copper and manganese from PN, advancement of enteral feeding, and the use of ursodiol (i.e., Actigall®); 5) At the time the diagnosis PNALD is made, the patient is expected to continue PN at least an additional 30 days.

Exclusion Criteria:

Other known causes of chronic liver disease (hepatitis C, cystic fibrosis, biliary atresia, and alpha 1 anti-trypsin deficiency).

c. Recruitment Methods

Omega-3 Fat Emulsion (Omegaven®)

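### In the second historical comparison, controls need two consecutive direct bilirubin values of at least 2.0 mg/dL and Omegaven patients need one; taken alone, this favours Omegaven by an unknown amount

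*Combined protocol and SAP*

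**What the plan says.** All references are to the combined protocol and SAP.

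- **Contemporary controls** (Follow up Study Utilizing Contemporary Historical Controls, inclusion criterion 3): "Present PNALD, as evidenced by two consecutive direct bilirubin" values of at least 2.0 mg/dL.
- **Omegaven group** (Patient Selection, inclusion criterion 2): PNALD "as defined as a direct bilirubin of ≥ 2 mg/dl or currently on Omegaven through another protocol". Criterion 3 reads: "Direct bilirubin > 2.0 mg/dl, or already on Omegaven through another protocol". Neither criterion asks for a repeat value.
- **Aim of the control selection** (same follow-up section): the procedure is meant "to make their selection process comparable to the prospectively enrolled Omegaven® cohort", and "we will apply the inclusion criteria to the records at moment that cholestasis develops (i.e., direct bilirubin ≥ 2 mg/dL"). The sentence goes on to rule out assumptions drawn from the later PN course.
- **Time zero** (Analysis of Baseline Characteristics): the last measurement before the first dose for Omegaven patients, and the first recorded direct bilirubin above 2 mg/dL for the historical control group. No separate baseline is given for the contemporary controls.
- **Endpoint** (Analysis of Efficacy of Omegaven): time from baseline to normalization, taken as the first of three consecutive values below 2 mg/dL. The outcomes section also accepts one low value plus weaning from PN.

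**The concern.** A confirming second value is observed after cholestasis first appears, and it belongs to the same series of measurements that decides the endpoint. Requiring it of one group selects that group on not having improved early. A control whose elevation is never confirmed is dropped. An Omegaven patient with the same history meets the written bilirubin criterion and can go on to be counted as a quick normalization.

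A second mechanism depends on the clock. If control time starts at the first value above 2, the stretch up to the second qualifying value is event-free for every control by construction, and Omegaven patients have no matching stretch.

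The protocol presents this cohort as more contemporary and less variable than the older one. The older controls enter on a single value ever above 2 mg/dL, so the comparison intended to be closer brings in a mismatch that the first one does not have. The Potential Study Limitations section does not mention it.

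**Working it through.** The plan gives no figure for this point, so there is none to reproduce. The check is a comparison of the criteria, followed by an illustration of size.

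**Step 1. Criteria side by side.**

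| Element | Contemporary controls | Omegaven |
|---|---|---|
| Bilirubin | two consecutive values ≥ 2.0 | one value, ≥ 2 (criterion 2) or > 2.0 (criterion 3), or already on Omegaven |
| Further PN expected | at least 30 days | at least 30 days |
| Standard therapies | failed | utilized |
| Time zero | not stated for this cohort; first value > 2 if the general rule applies | last measurement before first dose |

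The PN-duration and prior-therapy filters appear on both sides, so they do not offset the bilirubin difference. Planned adjustment for baseline bilirubin cannot bring back controls who were never selected.

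**Step 2. Inputs for the illustration.** From the protocol: 50 contemporary controls. Assumed: 50 Omegaven patients, no treatment effect, exponential resolution with median 90 days, 14 days between first and second value, and a transient share f of 0 to 30%. The older cohort was abstracted at two-week intervals; no interval is given for this one. The illustration also assumes that every transient case reaches Omegaven treatment and counts as an event. That assumption makes the effect large.

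**Step 3. What happens by day 14.** Among non-transient patients, the share resolving within 14 days is 1 − 2^(−14/90) = 0.102. At f = 20%:

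- Omegaven: 0.20 + 0.80 × 0.102 = 0.282, or 50 × 0.282 ≈ 14 early events.
- Controls, clock at second value: 50 × 0.102 ≈ 5.
- Controls, clock at first value: 0, by construction.

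The gap from 14 to 5 is due to the filter. The gap from 5 to 0 is due to the clock.

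**Step 4. Simulated hazard ratio for normalization, no true effect (above 1 favours Omegaven).**

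| Transient share f | Control clock at second value | Control clock at first value |
|---|---|---|
| 0% | 1.00 | 1.14 |
| 10% | 1.09 | 1.22 |
| 20% | 1.24 | 1.39 |
| 30% | 1.41 | 1.58 |

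A repeat with 365 days of follow-up agreed to within 0.1. Across the four rows, the nominal 5% test rejected in about 9, 19, 37 and 61% of runs with the clock at the first value (50 per group), and in about 7, 8, 16 and 32% with the clock at the second value (run with 40 per group). With the same rule and clock in both groups the hazard ratio was 1.00 and rejection about 5%.

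**Step 5. Different assumptions.** This version used weekly values, median resolution of 8, 16 or 26 weeks, 52 weeks of follow-up and 50 per group. It gave about 1.0 at f = 0, 1.10-1.14 at 10%, 1.21-1.32 at 20% and 1.35-1.50 at 30%. Direction and order of size are the same.

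**The case against.** A reader might infer that transient cholestasis is removed from the controls and kept in full in the Omegaven group, so that the comparison is biased toward Omegaven by a known amount. The documents do not support that, for five reasons.

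- **An isolated elevation does not bar a child for good.** The control criterion does not say the two values must be the first two. The Recruitment Methods section selects on ever presenting with cholestasis. A child with one unconfirmed elevation can qualify later, so only those never confirmed are lost.
- **Omegaven patients do not start at their first elevated value.** They are referred after diagnosis and reviewed by a multidisciplinary team, with further biochemistry as needed. Non-experimental options are looked at first. Their clock starts at treatment, and some transient elevations would plausibly have resolved by then. This screening is informal, however, and cannot be assumed to match a written two-value rule.
- **One low value is not a success.** Normalization needs three consecutive low values, or one plus weaning from PN, in children expected to need PN for at least 30 more days.
- **The clock effect is conditional.** The baseline definition refers to the historical control group, and nothing says which of the two values starts the contemporary clock. Without that effect, the illustration shows no bias at f = 0.
- **Another bias runs the other way.** The plan expects Omegaven patients to have more severe disease than controls, which would work against Omegaven. The net direction is not established.

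These points limit the size and the certainty. They do not remove the one-sided written filter or its conflict with the stated aim of comparable selection.

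**Conclusion.** The concern holds in a limited form. In the second analysis only, the written entry rules differ on a variable tied to the endpoint, and this contradicts the section's own aim. The mismatch and its direction taken alone are clear from the text. The size is not, because the transient share appears nowhere in the documents. The net bias is also unknown, because informal screening and greater severity in the Omegaven group may reduce or offset the effect. The hazard ratios of about 1.0-1.4 (clock at second value) and 1.1-1.6 (clock at first) rest on the assumptions in the working and show what the filter could do. They do not estimate the bias in this study. The point should be settled before this comparison is analysed, since the difference in rules can be removed by definition and cannot be adjusted away afterwards.

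**What to change.** For this comparison, write one bilirubin entry rule for both groups. This concerns who is analysed, not who is treated.

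1. Preferred: analyse Omegaven patients who had two consecutive pre-treatment direct bilirubin values ≥ 2 mg/dL, and set control time zero at the second qualifying value. State that Omegaven time still starts at treatment, so the two clocks are closer but not identical.
2. Sensitivity analysis: a single-value rule in both groups.
3. State that patients already on Omegaven through another protocol, or referred without two pre-treatment values, are left out of the matched-rule analysis, and report how many.
4. Reconcile ≥ 2 with > 2 between the two Omegaven criteria, the control criteria and the baseline definition.
5. Report how many otherwise eligible soybean patients were excluded for lack of a confirming value. This gives the missing transient share for the controls.

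Cost: SAP wording and analysis time. The plan already intends to examine bilirubin before baseline, so much of the data should be to hand. The downside is that an unknown number of Omegaven patients leave this secondary comparison, which lowers its precision.

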2.1 – Our primary hypothesis is that, after reaching bilirubin levels > 2 mg/dL, patients receiving Omegaven® will reach a bilirubin level ≤ 2 mg/dL faster than patients receiving conventional fat emulsions. Additionally, while patients receiving Omegaven™ will experience a decrease in their levels of bilirubin and other hepatic enzymes over time, patients receiving conventional emulsions will maintain high levels of bilirubin and other hepatic enzymes over time.

2.2 – Patients with surgical gastrointestinal disease and cholestasis will have better clinical hepatic outcomes than patients receiving conventional emulsions.

2.3 – Since patients receiving Omegaven® will have improved immune function, they will have a lower infection rate than patients receiving conventional fat emulsions.

2.4 – Due to a better general hepatic condition, patients receiving Omegaven® will also experience lower occurrence of liver transplant, death from hepatic associated causes, and blood transfusions.

2. Background and Significance

Parenteral Nutrition Associated Liver Disease (PNALD)

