Assessment of the effect of treatment will be based on a non-randomized, open-labeled, prospective study of intravenously administered Omegaven[®] fat emulsion to determine safety and preliminary efficacy in the treatment of PN associated liver injury. This treatment group will be compared to a group based on historical controls, i.e., a subset of patients (those whose direct bilirubin levels was ever > 2 mg/dL) previously studied by Andorsky et al.(31) This study included neonates treated between 1986 and 1996 who depended on parenteral nutrition for at least 90 days after surgical therapy for congenital or acquired intestinal diseases. Our study will primarily follow the patients included in Andorsky et al. study from 2 months before direct bilirubin first reached a level > 2 mg/dL (baseline date) until 2 months after patients either reached 3 consecutive bilirubin levels \leq 2 mg/dL or reached one bilirubin level \leq 2 mg/dL and were weaned from PN died, or underwent a liver transplant. In our exploratory analyses, we will include the entire available follow-up time in Andorsky et al. dataset for each patient.

b. Patient Selection and Inclusion/Exclusion Criteria

Omega-3 Fat Emulsion (Omegaven[®])

After the diagnosis of PNALD is made, patients who are followed by the Clinical Nutrition Service (CNS) or General Surgery Program, in conjunction with the patient's primary physician, will contact [name] or [name] and an evaluation will be performed. Cases may also include referrals of patients with PNALD from other healthcare facilities or self-referrals. If the patient's parents or guardians agree to participate in the study, informed consent will be obtained. The history of present illness and past medical history will be reviewed with the guardian and pertinent demographic and medical information will be recorded on data collection forms. This form will be used to record all laboratory results, nutritional history, and descriptions of any liver biopsies performed.

Though most patients receiving parenteral nutrition do not develop end stage liver disease, there is a small percentage of patients, typically infants and children on prolonged courses of parenteral nutrition, who do go on to develop fulminate liver failure. The study population of this protocol is limited to patients felt to fulfill any one of the following conditions:

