All patients receiving parenteral nutrition are followed by the Clinical Nutrition Service. Eligibility for the trial will be discussed on rounds. Prior historical and physical information, imaging studies, biopsies, and other available specialized tests will be reviewed by the multidisciplinary team experienced in the diagnosis and treatment of parenteral nutrition associated liver disease. Additional biochemical monitoring will be performed as necessary. If the patient's status supports consideration of treatment, the option for non-experimental therapy will be investigated. A similar process will be utilized for self-referrals and potential patients referred from distant healthcare facilities.

Soybean based Fat Emulsion (Intralipid[®] and/or Liposyn[®])

The conventional PN comparison group will be selected from patients previously studied by Andorsky et al.(31) We will study the subset of those patients whose recorded direct bilirubin was ever > 2 mg/dL. Information about these patients will be extracted from the Excel database used for this study and provided to us by the study's Principal Investigator, [name]. A request for research limited to the use of medical records/charts and computer databases was submitted and approved by the Committee on Clinical Investigations on January 17, 2007 (M07-01-0030).

Inclusion Criteria:

Andorsky et al. reviewed medical records of patients who were born at Children's Hospital Boston from 1985 to 1996 and who received a diagnosis of short bowel syndrome at most 30 days after birth (in the neonatal period). Short bowel syndrome was defined as dependence on PN for at least 90 days for diagnosis resulting from congenital intestinal malformations and/or intestinal resection.

Exclusion Criteria:

Patients with incomplete medical records (10 patients briefly seen for a second opinion) were excluded from the Andorsky et al. study. For our study, we will further exclude the subset of patients whose direct bilirubin was never > 2 mg/dL at any time during their follow-up times.

Follow up Study Utilizing Contemporary Historical Controls

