Because both Intralipid® and Liposyn® II are isotonic, both could be infused through either a central or peripheral line. Both products are compatible with parenteral nutrition solutions and were co-infused via y-site. Source container hang times varied during this period, and IFE was either infused from a single container over 24 hours or the container was changed every 12 hours per CDC recommendations. Also during this period, the administration method of PN changed. Prior to 1999, standard 0.2 micron inline filters were used routinely and only PN but not IFE could be infused through them (IFE was infused via y-site beneath the filter). After 1999, 1.2 micron filters became the standard inline filter, allowing for IFE to be filtered along with the PN solution.

Duration of Therapy

Patients remained on either Liposyn® II or Intralipid® until weaned from PN.

Discontinuation of Therapy

Patients at risk for malnutrition or resumption of PN were typically followed by the Clinical Nutrition Service for several months following discontinuation of PN.

ADDITIONAL PREDICTORS OF INTEREST

Since decisions about starting Omegaven® administration will follow a compassionate protocol, we expect that patients receiving Omegaven® will present more severe liver disease than the controls from the historical cohort. Therefore, to correct confounding biases, we anticipate the need to adjust for potential predictors of liver outcomes at baseline. Baseline will be defined as: the date that treatment starts for Omegaven® patients and on the date that patient reached bilirubin levels > 2 for soybean based fat emulsion patients.

The following predictors of liver disease will be considered:

- Baseline direct bilirubin levels.
- Diagnosis of Necrotizing Enterocolitis (vs. any other disease)
- Gender (male vs. female)
- Age (≥ 8 months vs. < 8 months)
- Gestational age
- Birth weight
- Race

To assess patients comparability, we will also descriptively explore trends in direct bilirubin level before the beginning of follow-up (start of treatment date for Omegaven® patients and date in which direct bilirubin level raised to > 2 mg/dL for control patients)

Subgroup Analysis

With exploratory purposes, we will describe safety and/or efficacy of Omegaven® in subgroups of patients including younger (vs. older) patients at baseline, patients who presented with infections (vs. who did not),

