Generally, primary safety analyses will be based on time from baseline or 30 days after baseline until two months after patients first reached direct bilirubin levels $< 2\text{mg/dL}$. Baseline will be defined as information collected at the date that treatment starts for Omegaven[®] patients and on the date that patient reached bilirubin levels > 2 for soybean oil fat emulsion patients. Information on mortality and transplant will be collected during the whole treatment with Omegaven[®] and during the whole period for which we have data available in the Andorsky et al. dataset. Primary efficacy analysis will include time from baseline until the patient normalizes bilirubin (presents three consecutive direct bilirubin $\leq 2\text{ mg/dL}$ or a direct bilirubin $\leq 2\text{ mg/dL}$ and weaned from TPN). With exploratory purpose, we will also describe the curve of the several markers for the entire period that Andorsky et al. recorded data.

Outcome/Endpoints

1. Treatment safety

Our primary outcome for treatment safety will be based on patient's essential fatty acid profile. We will compare patients before treatment with Omegaven[®] started and after treatment started (one month after treatment started until treatment stopped) with respect to the frequency with which triene/tetraene ratio > 0.2 at any time. We will also compare the occurrence any event of of hypertriglyceridemia (serum triglyceride $> 400\text{mg/dL}$) between Omegaven[®] and soybean oil fat emulsions. Primary analyses for these and all other safety outcomes will be based on a follow-up time for Omegaven[®] and soybean oil fat emulsions starting 30 days after baseline, i.e., 30 days after treatment started for Omegaven[®] patients and 2 months after the first direct bilirubin level $< 2\text{ mg/dL}$ was recorded. We will also explore comparisons including the time from baseline until the end of follow-up period.

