Analysis of Baseline Characteristics

For statistical purposes, baseline values will be defined as the last measurement before starting to administer Omegaven® for patients, in the treatment group, and as the measurement taken when a patient first had a direct bilirubin level > 2 mg/dL recorded, in the historical control group. Descriptive statistics for all baseline relevant risk factors will be summarized for Omegaven® (omega-3 based fat emulsion) and historical control (soybean oil fat emulsion) groups. Associations between categorical predictors and Omegaven® vs. soybean oil fat emulsion groups will be tested through chi-square tests. Associations between continuous predictors and treatment groups will be studied through means (and standard deviations) and t-tests, or medians (and interquartile ranges) and Wilcoxon tests, when appropriate.

Analysis of Safety and Tolerability of Omegaven®

All primary safety and tolerability analyses will be based on descriptive statistics. In secondary analyses, we will also assess the statistical significance of differences. Some safety and tolerability outcomes will be measured only in the Omegaven® group. For those, we will compare results before starting PN with Omegaven® (while receiving PN with soybean oil fat emulsions) with after starting PN with Omegaven®. The period receiving Omegaven® will start to be counted 30 days after beginning PN with Omegaven® for the main analysis. Outcomes measured in the Omegaven® and soybean oil fat emulsion groups will be described separately for each of those groups for a period starting 30 days after baseline, i.e., 30 days after starting PN with Omegaven®, for the treatment group, and 30 days after bilirubin > 2 mg/dL, for the soybean oil fat emulsion group.

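### The primary efficacy clock starts at treatment for Omegaven but at first direct bilirubin above 2 mg/dL for controls; nothing in the available text aligns the two, so the null hazard ratio can depart from 1 in either direction

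*Combined protocol and SAP*

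**What the plan says.** - **Time origin.** Additional Predictors of Interest: "Baseline will be defined as: the date that treatment starts for Omegaven® patients and on the date that patient reached bilirubin levels > 2"; the second date applies to the controls. The outcomes section and Analysis of Baseline Characteristics repeat the rule. The latter takes baseline values from "the last measurement before starting to administer Omegaven" in the treated group and from the first recorded direct bilirubin above 2 mg/dL in controls.
- **Use of that origin.** The outcomes section: "Primary efficacy analysis will include time from baseline until the patient normalizes bilirubin". Analysis of Efficacy applies Kaplan-Meier curves, log-rank tests and Cox models with baseline covariates. Death or transplant before normalisation is given an infinite time, and a comparison analysis leaves those patients out.
- **Hypothesis 2.1.** "after reaching bilirubin levels > 2 mg/dL, patients receiving Omegaven® will reach a bilirubin level ≤ 2 mg/dL faster than patients" on conventional emulsions. This describes one shared starting event.
- **Control selection.** The design section: "This study included neonates treated between 1986 and 1996 who depended on parenteral nutrition for at least 90 days". The control inclusion criteria: "Short bowel syndrome was defined as dependence on PN for at least 90 days". Omegaven patients must be PN dependent with an expected 30 or more further days, must already have used standard therapies, and may already be on Omegaven under another protocol.
- **Route to treatment.** For in-house patients, "Eligibility for the trial will be discussed on rounds"; outside referrals and self-referrals are also accepted. The time from first value above 2 to treatment start is not given.
- **Limitations.** Potential Study Limitations calls non-comparability the main weakness and says differences in severity would reduce the apparent effect. It discusses neither the time origin nor the 90-day selection.

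**The concern.** Each group is followed from a different point in the disease and is selected on getting through a different stretch of time. An Omegaven patient must be alive, untransplanted and (unless already on Omegaven) still cholestatic when treatment begins. A control whose bilirubin first passed 2 before PN day 90 must have stayed alive and on PN to that day. The time to normalisation counted from these two dates need not have the same distribution even if the emulsions act identically.

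At stake is the primary efficacy result. A hazard ratio different from 1 could reflect the clocks and the selection, and the statement on severity might lead a reader to treat a positive result as conservative.

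**Working it through.** The plan states no sample size, event count, hazard ratio or power for the efficacy comparison, so there is no figure of its own to reproduce. All inputs below other than the time origins, the 90-day rule and the handling of deaths are assumptions. Every scenario has no drug effect. A hazard ratio above 1 favours Omegaven.

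**1. Shift of origin alone.** Let time from first value above 2 to normalisation be Weibull with shape k and median 120 days (scale = 120/(ln 2)^(1/k)), and let treatment start D days after onset in patients not yet normalised. At u days on the plan's clock an Omegaven patient is u + D days from onset and a control is u days from onset, so

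hazard ratio at u = ((u + D)/u)^(k − 1).

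At u = D = 60 this is 2^(k − 1): 0.87 for k = 0.8, 1.00 for k = 1, 1.41 for k = 1.5. The Cox estimates over 365 days are:

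| Shape k | D = 14 | D = 30 | D = 60 | D = 90 |
|---|---|---|---|---|
| 0.8 (falling hazard) | 0.93 | 0.90 | 0.85 | 0.82 |
| 1.0 (constant) | 1.00 | 1.00 | 1.00 | 1.00 |
| 1.25 | 1.05 | 1.11 | 1.18 | 1.24 |
| 1.5 (rising) | 1.10 | 1.21 | 1.38 | 1.54 |

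A constant hazard that varies between patients (gamma frailty variance 0.5 to 1.0, D = 30 to 90) gives 0.92 down to 0.70. The more extreme shapes 0.6 and 2.0 reach 0.65 and 2.39 at D = 90.

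**2. The 90-day rule acting through weaning.** Take exponential normalisation (mean 240 days) and exponential weaning (mean 150 days), either one ending the wait. If onset is on PN day 30, a control cannot be weaned for the next 60 days. During that time the ratio is (1/240 + 1/150)/(1/240) = 1 + 240/150 = 2.6; afterwards it is 1. The Cox average is 1.39, falling to 1.07 if onset is on PN day 80. If every Omegaven patient truly needs 30 more PN days, the range is 1.17 to 0.89.

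**3. The 90-day rule acting through death.** Take a constant normalisation hazard (median 20 weeks), early deaths (Weibull shape 0.5, scale 100 weeks), a mean wait of 8 weeks and onset on average 4 weeks after PN start. Deaths get infinite time, as planned. The hazard ratio is 1.29 without the 90-day rule and 0.83 with it. With shape 1.5 it is about 1.56 without and 0.98 with. The rule can therefore raise the ratio (step 2) or lower it (step 3).

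**4. Does planned adjustment repair it?** Time since onset is not a listed covariate, and baseline bilirubin is measured at different disease times in the two groups. With waits of 14 to 90 days and bilirubin assumed to rise after onset, mean baseline was 2.9 mg/dL in controls and 5.7 to 5.9 in Omegaven patients. Adjusting for it changed 1.27–1.29 to 1.25–1.41 (shape 1.5) and 0.87–0.89 to 0.86–1.05 (shape 0.8).

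**5. Does a common clock repair it?** For the shift alone, time since onset with delayed entry gave 0.99–1.00 in all 24 scenarios (shapes 0.6 to 2.0, D = 14 to 90). With the 90-day rule, and controls entering at the later of onset and PN day 90, it stayed within 0.97–1.03 when weaning did not alter the normalisation rate and the wait was unrelated to prognosis. When weaning raised that rate three- to six-fold the range was 0.82–1.22, sometimes further from 1 than the planned analysis (in one case 1.04 became 1.17). When the wait depended on the patient's own prognosis it was 0.86–1.25.

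**The case against.** The strongest reply is that this is preliminary efficacy in a compassionate-use study which already names non-comparability as its main limitation. The plan adjusts for baseline bilirubin and age, describes bilirubin trends before baseline, and fits longitudinal models from two months before baseline with equal pre-treatment slopes. It repeats the comparison without deaths and transplants. It adds a 1999–2004 cohort with criteria applied when cholestasis develops and no 90-day rule. In-house patients may start treatment within days, and a short lag or a constant hazard produces little bias.

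Much of this is fair. It limits how firmly any size can be stated, and the scenario ranges should not be read as estimates. It does not remove the point: none of those measures gives the primary comparison one origin, the second cohort removes the 90-day selection from its own analysis only, and whether the lag is short is not documented.

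The reply is also right that a common clock is no cure. Selection on 90 days of PN may be selection on prognosis, and the onset date is measured more coarsely in controls: their data were abstracted at two-week intervals, while Omegaven patients with raised bilirubin are tested weekly.

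**Conclusion.** The concern holds in this form: the origins differ, the selection differs, nothing in the available text aligns them, and the null hazard ratio can lie on either side of 1. Size and direction are unknown. Roughly 0.7 to 1.5 is what moderate assumptions about lag, hazard shape, frailty, weaning and death produce, and some give almost exactly 1. Part of the text just before the study design section was not available, so the conclusion is limited to what was.

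Three stronger readings are not supported.

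- A reader might infer a bias in favour of Omegaven of the familiar immortal-time kind. The event-free wait is not credited to Omegaven, because its clock starts at treatment, and the scenarios go both ways.
- A reader might infer the opposite, that the bias is conservative, from the limitations section. That statement concerns severity and does not cover the clock or the 90-day rule.
- A reader might expect the aligned analysis to be close to unbiased. That holds only if weaning does not change the normalisation rate and the wait is unrelated to prognosis; otherwise its simulated null hazard ratio was about 0.8 to 1.25.

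This should be fixed, by an added analysis and by reporting; it does not invalidate the study.

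**What to change.** 1. Pre-specify one sensitivity analysis beside the planned one. Measure time since first direct bilirubin above 2 in both groups; Omegaven patients enter the risk set at treatment start, and primary controls at the later of that first value and PN day 90. Do not add Omegaven pre-treatment time to the control group: it is event-free by selection.
2. In one version keep the planned handling of death and transplant, so that any difference can be attributed to the clock. Show cause-specific censoring separately.
3. Report the distribution of the lag from first value above 2 to Omegaven start, the number with that date missing, and the overlap of baseline bilirubin between groups.
4. Use one endpoint definition. The outcomes section accepts three consecutive values at or below 2, or one such value plus weaning; Analysis of Efficacy requires three values below 2 and has no weaning route. The effect of the 90-day rule depends on which applies.
5. For patients already on Omegaven under another protocol, state whether the start date is the original start or enrolment here.
6. Use the same clock for the 1999–2004 cohort, with controls entering when they meet its criteria.
7. State in the limitations that this bias has unknown direction.

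**Cost.** SAP wording, onset dates for Omegaven patients (pre-baseline bilirubin is already to be examined) and PN start dates for controls. Some referral onset dates may be missing, control dates are coarse, and control time before PN day 90 is lost. In the simulated scenarios with 30 per group the standard error of the log hazard ratio rose by 5–23%. Confounding by severity and by referral remains.
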